**Document Date: 02/05/2017** 

## **Study Protocol**

The study was a single-blind randomized clinical trial with parallel group and allocation ratio was 1:1. This study was approved by the Clinical Research Institutional Review Board (No. 2017/53). The study was performed at the Department of Orthopaedics and Traumatology, Turgut Ozal Medical Hospital, Inonu University. Informed written consent was obtained from all participants' parents or legal guardians. The patients who met the inclusion criteria randomly assigned into two groups (Rehabilitation group, Mobilization group) in a ratio of 1:1 through the stratified block randomization method. The patients and the researcher who were responsible for the analyzing of the data were blinded to the randomization results. All data were collected at baseline, 1 week and 6 weeks (only quality of life).

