## **Statistical Analysis Plan**

The SPSS (version23; SPSSInc., Chicago, IL, USA) was used to conduct the analysis. Descriptive statistics were presented as mean  $\pm$  standard deviation and percentage. Suitability of variables to normal distribution were analyzed using visual (histogram and probability graphics) and analytical methods (Shapiro-Wilk Test). The differences between both groups were assessed by Chi-squared, Fisher's final test and independent sample t test. Split plot ANOVA was used to compare the pretreatment and posttreatment assessments at baseline, 1 week/6 week in both groups (group: rehabilitation vs mobilization; time: baseline vs 1 week/6 week). VAS, thorax mobility, trunk balance, 2MWT and SRS-22 scales were analyzed for both groups using the split plot ANOVA. A p value of <0.05 was considered to be significant.

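### Randomisation is stratified, but the split plot ANOVA for all five outcomes omits the strata, so the test is conservative and loses power wherever the strata predict the tested contrast

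*Combined protocol and SAP*

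**What the plan says.** The Study Protocol section describes a two-arm trial with "parallel group and allocation ratio was 1:1", randomised "in a ratio of 1:1 through the stratified block randomization method". It does not name the stratification factors, the number of strata or the block size.

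The Statistical Analysis Plan section states that "VAS, thorax mobility, trunk balance, 2MWT and SRS-22 scales were analyzed for both groups using the split plot ANOVA", and gives the factors of that model as "group: rehabilitation vs mobilization; time: baseline vs 1 week/6 week". It also says that "The differences between both groups were assessed by Chi-squared, Fisher's final test and independent sample t test"; none of these tests is stratified either. No stratum term or covariate appears anywhere in the plan. The plan does not say whether the group main effect or the group-by-time interaction is the test of treatment.

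On timing, the protocol says "All data were collected at baseline, 1 week and 6 weeks (only quality of life"). On significance, the SAP says "A p value of <0.05 was considered to be significant". No sample size, power target, standard deviation or effect size is given.

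**The concern.** Blocking within strata forces the arms to be nearly equal in stratum composition. Differences between strata then contribute almost nothing to the chance variation of the group difference. An analysis that ignores the strata still counts those differences as error, so it reports a standard error larger than the true one.

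Two things are at stake: calibration (the actual type I error falls below the nominal 5%) and efficiency (the precision that stratification provides is not used). There is no bias in the estimate and no excess of false positives.

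Whether this bites depends on which term is tested. A stratum effect on change stays in the residual of the group-by-time test, and a stratum effect on level stays in the residual of the group main effect. A stratum effect that is constant over time drops out of group-by-time.

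**Working it through.** The plan states no figure that could be reproduced, so the check starts from the design.

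**Inputs from the documents.** 1:1 allocation in stratified blocks and two assessments for most outcomes (Study Protocol); group and time as the only model factors, and a 0.05 threshold (Statistical Analysis Plan). Two-sided testing is assumed.

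**Inputs assumed.** R² is the share of variance of the *tested contrast* explained by the strata, taken as 5, 10 and 20%. The reference power of 80% for the adjusted analysis is also assumed.

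**Step 1: what the model tests.** With two time points, the group-by-time F equals the squared two-sample t on within-patient change. On a simulated data set of 40 patients both were 0.5348. Adding the same stratum shift at both times left the value at 0.5348. The group main effect is a t test on each patient's mean over the two times.

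**Step 2: size of the effect.** With near-perfect balance within strata, true SE / reported SE = √(1 − R²). Hence:

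- SE overstatement = 1/√(1 − R²) − 1
- type I error = 2 × [1 − Φ(1.96/√(1 − R²))]
- power = 1 − Φ(1.96/√(1 − R²) − 2.80)
- sample-size ratio to regain 80% without adjustment = [(1.96/√(1 − R²) + 0.842)/2.80]²

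| R² | 1.96/√(1 − R²) | SE overstated | Type I error | Power (adjusted = 80%) | Extra patients |
|---|---|---|---|---|---|
| 5% | 2.011 | 2.6% | 4.4% | 78.5% | 3.7% |
| 10% | 2.066 | 5.4% | 3.9% | 76.9% | 7.7% |
| 20% | 2.191 | 11.8% | 2.8% | 72.9% | 17.2% |

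**Step 3: simulation check.** This used permuted blocks of 4, two or four equal strata, assumed totals of 32 to 80 patients and 100,000 replicates per setting. For R² = 5, 10, 20%:

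- Unadjusted: type I error 4.4–4.5%, 3.8–4.1% and 2.8–3.1%; power 78.3–78.8%, 76.6–77.0% and 72.3–72.9%.
- Stratum-adjusted: type I error 4.9–5.1%; power 79.4–80.2%.

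A separate simulation fixed the effect at 0.89 total SD with 20 per arm (both assumed). At R² = 10% type I error was 3.9% unadjusted against 5.0% adjusted, and power 78.9% against 81.9%. At R² = 20% type I error was 2.9% against 4.9%, and power 80.1% against 86.3%. At R² = 0 power was 77.9% either way.

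**Step 4: by term.** Assume a within-stratum correlation of 0.5 between baseline and follow-up, and a follow-up variance of 1 of which the strata explain 10%, so the within-stratum variance is 0.9 at each time.

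- Change: within-stratum variance 0.9 × 2 × (1 − 0.5) = 0.9. A stable stratum effect adds 0, so R² = 0. An effect at follow-up only adds 0.1, so R² = 0.1/1.0 = 10%.
- Two-time mean: within-stratum variance 0.9 × (1 + 0.5)/2 = 0.675. A stable effect adds 0.1, so R² = 0.1/0.775 = 12.9%. A follow-up-only effect adds 0.1/4 = 0.025, so R² = 0.025/0.7 = 3.6%.

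With 20% in place of 10%, R² for the mean is 0.2/0.8 = 25.0% (stable) and 0.05/0.65 = 7.7% (follow-up only).

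Simulated type I error, assumed total n = 40, two strata:

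| Stratum effect | Group-by-time | Group main effect |
|---|---|---|
| Stable, 10% (20%) of level | 5.1% (5.0%) | 3.7% (2.4%) |
| Follow-up only, 10% (20%) | 3.9% (2.9%) | 4.6% (4.0%) |

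**The case against.** The strongest reply is that the loss may be zero for the test that matters. Group-by-time is the natural treatment test in a pre/post design. Strata are usually chosen because they predict level, and a stable effect on level cancels there. Nothing in the plan suggests that the strata predict change. The group main effect averages in the untreated baseline and is a poor treatment test whatever is done about strata. This stands as a limit on the size of the problem. It does not remove it, because the plan does not say which term is tested and does not name the strata, so a reader cannot rule out either route to a loss.

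It is also fair that R², the numbers of patients and strata, the block size and the correlation are all assumed, and that the range for R² includes zero. At R² of 5 to 10% the loss is only 1.5 to 3.1 points of power (80 − 78.5 and 80 − 76.9). The 17.2% sample-size penalty needs strata that explain 20% of the tested contrast. Because the error is only conservative, no positive finding is made unsafe.

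Two smaller points also stand. The plan mentions no confidence intervals, so over-wide intervals would matter only if intervals are reported. SRS-22 may have three time levels rather than two; the equivalence with a t test on change, and the figures by term, would then not carry over directly, although adding strata and strata-by-time would still be the remedy.

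**Conclusion.** The concern holds. The plan randomises within strata and analyses without them, for all five outcomes. If the strata explain 5 to 20% of the variance of the tested contrast, the standard error is overstated by 2.6 to 11.8%, type I error falls to between 4.4% and 2.8%, and 1.5 to 7.1 points of power are lost against an adjusted analysis with 80%. If the strata do not predict that contrast, nothing is lost.

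The direction follows from the design; the size in this trial cannot be fixed from the documents. Absolute underpowering cannot be shown, because no sample size or power target is stated. This is a flaw of efficiency and calibration, not of validity, and it should be corrected because the remedy costs so little.

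**What to change.** - Name the stratification factor(s), and state which term is the treatment test (group-by-time if the split plot ANOVA is kept).
- Add the stratification factor(s) and their interaction with time to the split plot ANOVA for each of the five outcomes. With two time points this is the same as regressing change on group and the stratification factor(s).
- State whether SRS-22 enters with two or three time levels.
- Set a rule in advance for merging any stratum too sparse to contain patients from both arms.

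An ANCOVA of follow-up on group, baseline and the stratification factor(s) is an alternative. Its baseline adjustment is a separate gain, not counted in the figures above.

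The cost is SAP wording and one or a few degrees of freedom; the strata are already held from randomisation. If they turn out not to be prognostic, the simulated price was at most about 0.5 points of power (assumed n = 40, four strata: 79.7% adjusted against 80.2% unadjusted).

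### Does the silence about who measured the outcomes, and whether they were masked to group, require a change to the plan?

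*Combined protocol and SAP*

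**What the plan says.** The Study Protocol section opens with "The study was a single-blind randomized clinical trial with parallel group and allocation ratio was 1:1". It then names two blinded parties: "The patients and the researcher who were responsible for the analyzing of the data were blinded to the randomization results". Data collection is described without naming anyone: "All data were collected at baseline, 1 week and 6 weeks (only quality of life"; the bracketed remark restricts the six-week visit to quality of life.

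The Statistical Analysis Plan section lists the outcomes and the method: "VAS, thorax mobility, trunk balance, 2MWT and SRS-22 scales were analyzed for both groups using the split plot ANOVA". Its decision rule is "A p value of <0.05 was considered to be significant". It also promises descriptive summaries as means with standard deviations. It mentions no confidence interval and no sensitivity analysis.

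**The concern.** The masking that protects a measured outcome is that of the person taking the measurement. The plan names the patients and the analyst and leaves that person out. Blinding the analyst cannot undo a distortion that is already in the recorded data. The single-blind label does not settle the matter either, because it sits beside two blinded parties.

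The gap would matter most for outcomes run by an examiner. The documents give no measurement procedures, but it is reasonable to assume that thorax mobility, trunk balance and the 2MWT are of that kind: three of the five outcomes. If VAS and SRS-22 are completed by the patient, the stated patient blinding covers them.

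With an unmasked examiner, a systematic difference between groups in coaching, reading or timing would be indistinguishable from a treatment effect. It could create an effect or conceal one. A bare p value would not tell the reader how large such a difference must be to overturn the finding.

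**Working it through.** **Inputs.** From the documents: 1:1 allocation, a 0.05 threshold, and a split plot ANOVA of group by time. Not in the documents: sample size, SD, effect size, the correlation rho between baseline and follow-up, and the size of any bias. There is therefore no figure in the plan to reproduce, and everything below is illustration. The test is taken as two-sided.

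**Model.** The three outcomes assumed to be examiner-run have two time points, because the six-week visit is for quality of life only. The group-by-time test is then a two-sample t test on change, with df = 2n − 2 for n per arm.

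**Step 1: false positives under bias.** With no true effect and a bias of b SD of change, the noncentrality is b × √(n/2). The rejection rates from the noncentral t are:

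| n per arm | b = 0.1 | b = 0.2 | b = 0.3 |
|---|---|---|---|
| 15 | 5.8% | 8.3% | 12.5% |
| 30 | 6.7% | 11.9% | 20.8% |
| 50 | 7.9% | 16.8% | 31.8% |

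**Step 2: bias in the opposite direction.** At 30 per arm, a true difference of 0.6 SD of change has 63% power. A bias of 0.2 leaves a net 0.4 and 33% power; a bias of 0.3 leaves a net 0.3 and 21%.

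**Step 3: choice of unit.** If the bias is measured in SDs of a single reading instead, it must be divided by √(2(1 − rho)). This equals 1 only at rho = 0.5. For rho from 0.3 to 0.7 and n from 15 to 50, the ranges become 7.3% to 24.8% (bias 0.2) and 10.3% to 48.3% (bias 0.3). That widening comes wholly from the unit: with bias in SDs of change, rho drops out and Step 1 stands.

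**Step 4: how much bias a result could absorb.** The smallest significant difference is t(0.975, 2n − 2) × √(2/n), which is 0.748, 0.517 and 0.397 SD of change at 15, 30 and 50 per arm. For an observed difference of 0.8, the margins are:

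- n = 15: 0.8 − 0.748 = 0.052
- n = 30: 0.8 − 0.517 = 0.283
- n = 50: 0.8 − 0.397 = 0.403

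If the 0.8 is in single-reading SDs, the critical value is multiplied by √(2(1 − rho)). At 15 per arm and rho = 0.3 the margin is 0.8 − 0.748 × 1.183 = −0.09, so the result is not significant even without bias. At rho = 0.7 it is 0.8 − 0.748 × 0.775 = 0.22. The margin changes sign on an input the documents do not give.

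**Step 5: what the margin adds.** The lower 95% limit is the difference minus t × SE, and SE is √(2/n) in SDs of change. At 30 per arm this is 0.8 − 0.517 = 0.283, the same number as the margin in Step 4. The bias that brings the nearer limit to zero is that limit, rescaled.

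**Step 6: what can be recovered anyway.** If the promised means are reported by group and visit, they give the difference in change. With two time points and an exact F or p value, SE is that difference divided by t, where t = √F. The interval then follows without any further analysis. The plan does not promise exact p values, so this depends on how the results are reported.

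**The case for a change.** The strongest case for a change is that the omission is plain on the page and cannot be put down to redaction, since both sentences are complete. It concerns the role that matters most for three of five outcomes, and it would cost only a few sentences to repair. A rule based on p alone also treats a result at p = 0.05, which can absorb no bias, like one at p = 0.001. There, by the normal approximation, bias could explain 1 − 1.960/3.291 = 40% of the effect before significance is lost. The request for a confidence interval is sensible, and patient blinding between a rehabilitation and a mobilization group is asserted without saying how it was kept.

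What stands is the factual part: the text does not identify the assessor or that person's masking, and an interval reads better than a p value. The step from there to a fault in the plan does not stand. An assessor not described is not an assessor shown to be unmasked. That a p value does not display absorbable bias is true of almost any plan, and the case for an interval is the same whether or not the assessors were masked. The study is described in the past tense with its data already collected, so wording added now cannot alter how the measurements were taken.

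**Conclusion.** No change to the plan follows. This is missing descriptive detail, of the kind authors supply when they report the trial: who assessed each outcome at the visits where it was measured, whether they were masked, and a limitation if they were not. A between-group difference with its interval can be given in the same place. Neither would alter the split plot ANOVA, the decision threshold or any result, and a tipping-point figure would remove no bias.

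The size cannot be fixed from the documents. The illustrative false-positive rates of 5.8% to 31.8% rest on an assumed 15 to 50 per arm, an assumed bias of 0.1 to 0.3 SD of change, and the assumption that an examiner ran the outcomes unmasked. If the assessors were masked, the bias at issue need not have arisen. The conclusion would be different if the documents stated that assessors knew the allocation, or if they contained a rule that depended on assessor masking; they do neither.

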## **Statistical Analysis Plan**

The SPSS (version23; SPSSInc., Chicago, IL, USA) was used to conduct the analysis. Descriptive statistics were presented as mean  $\pm$  standard deviation and percentage. Suitability of variables to normal distribution were analyzed using visual (histogram and probability graphics) and analytical methods (Shapiro-Wilk Test). The differences between both groups were assessed by Chi-squared, Fisher's final test and independent sample t test. Split plot ANOVA was used to compare the pretreatment and posttreatment assessments at baseline, 1 week/6 week in both groups (group: rehabilitation vs mobilization; time: baseline vs 1 week/6 week). VAS, thorax mobility, trunk balance, 2MWT and SRS-22 scales were analyzed for both groups using the split plot ANOVA. A p value of <0.05 was considered to be significant.

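### Every scale is tested by split-plot ANOVA with baseline as a time level; an ANCOVA on the baseline already collected would usually be more precise, at almost no cost

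*Combined protocol and SAP*

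**What the plan says.** The Statistical Analysis Plan names one model for the repeated measurements: "Split plot ANOVA was used to compare the pretreatment and posttreatment assessments at baseline, 1 week/6 week in both groups". Its factors are "group: rehabilitation vs mobilization; time: baseline vs 1 week/6 week", and it covers every scale: "VAS, thorax mobility, trunk balance, 2MWT and SRS-22 scales were analyzed for both groups using the split plot ANOVA". Baseline is thus one of the levels of time, not a covariate.

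The only other comparative sentence is "The differences between both groups were assessed by Chi-squared, Fisher's final test and independent sample t test". It names no outcome, time point or covariate, so it supplies no baseline adjustment. The plan does not say which ANOVA effect (group, time or their interaction) is the treatment test, and it mentions no between-group difference with a confidence interval.

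The Study Protocol section gives the visits as "All data were collected at baseline, 1 week and 6 weeks (only quality of life)", the design as a "single-blind randomized clinical trial with parallel group and allocation ratio was 1:1", and the allocation method as "in a ratio of 1:1 through the stratified block randomization method". It does not name the stratification factors.

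**The concern.** In a randomised comparison, the natural treatment test in this model is group-by-time. VAS, thorax mobility, trunk balance and 2MWT have only baseline and 1 week. SRS-22, on the natural reading, has baseline and 6 weeks. With two levels the interaction compares mean change between the groups, which subtracts the whole of each patient's baseline value. That is the best weight only when the true slope of follow-up on baseline is 1. At any other slope the same data allow a narrower interval and more power.

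Chance imbalance also matters. If the groups happen to differ at baseline, the change score over-corrects when the slope is below 1 and under-corrects when it is above 1. This is a shift conditional on the observed imbalance; averaged over randomisations it is zero.

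**Working it through.** **Inputs.** From the documents: two groups, 1:1 allocation, baseline collected, and the threshold "A p value of <0.05 was considered to be significant" (sidedness not stated; two-sided assumed). The documents give no sample size, SD, effect size or correlation, so there is no planned figure to reproduce. Assumed over a range: ρ, the baseline-to-follow-up correlation, and k = baseline SD / follow-up SD.

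**1. Equivalence.** In one simulated data set with 20 per arm and two time levels, the group-by-time F was 3.6308 and the squared change-score t was 3.6308. The group main effect gave F = 0.3356; it tests the average of baseline and follow-up, which is a different question. With three time levels the interaction has 2 degrees of freedom (F = 2.226) and matches neither squared change-score t (3.631 and 3.848).

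**2. Large-sample variances**, in units of the follow-up variance:

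- change score: 1 + k² − 2kρ
- ANCOVA: 1 − ρ²
- difference: (k − ρ)² ≥ 0, which is zero only when the slope ρ/k equals 1

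With equal SDs (k = 1) the ratio of ANCOVA to change-score variance is (1 − ρ²)/(2 − 2ρ) = (1 + ρ)/2. With 1:1 allocation the pooled ANCOVA slope minimises the summed variance of the two arms, so the ordering holds even if the slopes differ by arm.

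**3. Size.** Variance ratio, with the interaction's power in brackets (normal approximation; effect set so that ANCOVA has 80%):

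| ρ | k = 0.8 | k = 1 | k = 1.25 |
|---|---|---|---|
| 0.3 | 0.784 (69.9%) | 0.650 (61.7%) | 0.502 (51.0%) |
| 0.5 | 0.893 (75.4%) | 0.750 (67.9%) | 0.571 (56.3%) |
| 0.7 | 0.981 (79.2%) | 0.850 (73.3%) | 0.628 (60.2%) |
| 0.9 | 0.950 (78.0%) | 0.950 (78.0%) | 0.608 (58.9%) |

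Example: ρ = 0.7, k = 1.25 gives (1 − 0.49)/(1 + 1.5625 − 1.75) = 0.51/0.8125 = 0.628. The change-score interval is wider by 1/√ratio − 1. At k = 1 that is 24.0%, 15.5%, 8.5% and 2.6%; over the whole grid it runs from 1.0% (ratio 0.981) to 41% (ratio 0.502).

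**4. Small samples.** Estimating the slope multiplies the ANCOVA variance by about 1 + 1/(N − 4), N being the total. At 10 per arm this is 1 + 1/16 = 1.0625, so at k = 1 the ratio becomes 0.75 × 1.0625 = 0.797 for ρ = 0.5 and 0.95 × 1.0625 = 1.009 for ρ = 0.9. Simulated power, interaction/ANCOVA (20,000 runs per setting; normal, complete data; k = 1):

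| ρ | 10 per arm | 20 per arm |
|---|---|---|
| 0.3 | 56.9/72.7% | 60.0/77.1% |
| 0.5 | 62.5/72.1% | 65.3/76.7% |
| 0.7 | 68.2/72.7% | 71.0/76.6% |
| 0.9 | 73.6/73.0% | 76.2/77.1% |

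In the worst setting tried for ANCOVA (ρ = k = 0.8, slope exactly 1) the pairs were 75.6/72.7% at 10 per arm, 78.3/77.1% at 20 and 79.4/78.9% at 40, a loss of 2.9, 1.2 and 0.5 points. Where type I error was checked (10 and 20 per arm), it was 0.047 to 0.051 for both methods.

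**5. Conditional shift.** For an observed baseline difference d, the change-score estimate is displaced by −(1 − ρ/k)d: −0.30d at ρ = 0.7, k = 1, and +0.125d at ρ = 0.9, k = 0.8.

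**The case against.** The strongest reply is that the planned test is valid, so this is a choice between two sound estimators, and nothing in the documents shows that the choice matters here. That stands: the gain could be very small for any of the five scales.

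Second, the equality with a change-score t test holds only for the interaction and only with two time levels. The plan names no effect, and quality of life may have been measured at all three visits. This also stands. If SRS-22 has three levels, the figures above do not apply to its 2-degree-of-freedom test. The other four scales are unaffected, and an unnamed treatment effect is itself a reason to specify an adjusted difference.

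Third, ANCOVA can lose slightly in a very small trial when the slope is near 1, and the simulations assume normal data, which is unverified for a bounded scale such as VAS. True, but the downside found was about 3 points at 10 per arm, against a large-sample gain of 12 to 18 points at ρ = 0.5 and 0.3 with equal SDs.

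Fourth, the plan is written in the past tense. If the analysis has been run, an ANCOVA is post hoc and cannot silently replace the planned test. That is right, and it governs how the result is labelled.

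**Conclusion.** The point holds as a recommendation on efficiency, not as a fault in validity. The plan collects a baseline for every scale and then uses it in a way that is asymptotically never more precise than ANCOVA and, unless the slope is close to 1, less precise. The ordering rests on randomisation and the stated 1:1 allocation. It concerns the two-level group-by-time comparison: securely for four scales, and for SRS-22 if its time factor is baseline and 6 weeks. The size for this trial is unknown, because every figure depends on assumed values of ρ, k and sample size.

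**What to change.** As the between-group analysis, report for each scale the adjusted mean difference with 95% confidence interval from an ANCOVA of the 1-week value (6-week value for SRS-22) on group and that scale's baseline. Add the randomisation stratification factors where they are few relative to the sample; the investigators must supply them. If SRS-22 was also measured at 1 week, name the 6-week baseline-adjusted difference as its contrast. Keep the split-plot means as description.

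This needs no extra patients, visits or data. SPSS, already the named software, fits the model, and the slope costs 1 degree of freedom. In the settings simulated, two binary factors with no prognostic value cost at most 1.4 power points at 10 per arm, 0.4 at 20 and 0.2 at 40; more factors or levels could cost more. If the analysis has not been run, this is a wording change. If it has, it is one re-analysis, labelled as such and reported beside the planned result.

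### The split plot ANOVA in SPSS, on its usual reading, drops from each outcome's model any child missing a visit in it, so each comparison is likely to be completers only

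*Combined protocol and SAP*

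**What the plan says.** The Statistical Analysis Plan names SPSS version 23 as the software that "was used to conduct the analysis", without naming a procedure. It gives one method for the follow-up outcomes: "Split plot ANOVA was used to compare the pretreatment and posttreatment assessments at baseline, 1 week/6 week in both groups". It then lists the outcomes: "VAS, thorax mobility, trunk balance, 2MWT and SRS-22 scales were analyzed for both groups using the split plot ANOVA". The factors are "group: rehabilitation vs mobilization; time: baseline vs 1 week/6 week".

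The Study Protocol section sets the visits: "All data were collected at baseline, 1 week and 6 weeks (only quality of life"). I take SRS-22 to be the quality-of-life measure, since no other listed outcome fits. The other four outcomes then have two visits (baseline and 1 week). SRS-22 has a 6-week visit and, on the natural reading, a 1-week visit as well, though this is not said outright.

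Patients were "randomly assigned into two groups (Rehabilitation group, Mobilization group) in a ratio of 1:1 through the stratified block randomization method". Neither section says which randomised patients enter the analysis, what happens when a visit is missing, or whether any sensitivity analysis is planned.

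**The concern.** A classical split plot ANOVA works on one complete row per patient. In SPSS its usual implementation, GLM Repeated Measures, removes a patient from every test in a model if any visit in that model is missing. With no rule to offset this, the default result is a completer analysis.

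Two things are at stake. The first is precision: scores already observed on a child are set aside. The second is comparability: if the children who leave differ between arms in ways related to their scores, the children left in the model are no longer the groups that randomisation formed. SRS-22 is the most exposed outcome because it alone is followed beyond 1 week.

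**Working it through.** The plan gives no sample size, SD, correlation or attrition, so there is no figure of its own to reproduce. The inputs below are assumptions for illustration: 20 per arm, SD 1 at each visit, between-visit correlation r = 0.5 unless stated, and 20% missing the last visit (16 per arm left).

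**1. Who is dropped, by outcome**

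| Child misses | SRS-22 model | Other four models |
|---|---|---|
| 6 weeks only, SRS-22 fitted as baseline and 6 weeks | dropped; baseline unused; no 1-week score was in the model | kept |
| 6 weeks only, SRS-22 fitted with three time levels | dropped; baseline and 1-week scores both unused | kept |
| 1 week | dropped if 1 week is a level | dropped; baseline unused |

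The slash in the SAP's description of the time factor allows either SRS-22 reading and does not settle which is meant.

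**2. Precision under random loss, two-visit outcomes.** The group-by-time test compares mean change between arms. Per-arm variance of mean change:
- Completers: 2(1 − r)/16 = 1/16 = 0.0625.
- Likelihood, keeping the baselines of children who were lost: (1 − r²)/16 + (1 − r)²/20 = 0.75/16 + 0.25/20 = 0.0594.
- SE ratio: √(0.0594/0.0625) = 0.975, a fall of about 2.5%.
- At r = 0.7: 0.0375 against 0.51/16 + 0.09/20 = 0.0364, a fall of about 1.5%.

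**3. Precision, 6-week SRS-22 with three visits observed.** Simulation (20,000 trials, equal correlations of 0.5) gave an SE of 0.356 for completers and 0.346 for the likelihood estimate, a fall of about 3%. With nobody lost the SE is √(2 × 1/20) = 0.316. The model therefore recovers about 0.010 of a 0.040 rise. The rest is lost under either method because the 6-week score is absent.

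**4. Precision, 1-week SRS-22 contrast, three-level reading only**
- All observed 1-week data: √(2 × 1/20) = 0.316.
- Completers to 6 weeks: √(2 × 1/16) = 0.354, which is 12% larger (simulated 0.355).
- Simulated at 10% and 30% loss: 0.333 and 0.382, which are 5% and 21% larger.

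Under the two-level reading none of these figures applies.

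**5. Bias.** Suppose loss in one arm depends on an observed score s, and completers' mean of s is shifted by δ. Completers' mean change from baseline to visit v is then shifted by (ρ_sv − ρ_s0) × δ, where ρ denotes the correlations. If the same happens in both arms, with no true effect, the shifts cancel.
- *Score-dependent loss in the rehabilitation arm only* (log-odds slope 1 per SD on the 1-week score, about 24% against 20% loss, δ about 0.21 SD). The 6-week bias is 0 with equal correlations. It is (0.7 − 0.5) × 0.21 = 0.04 SD if weeks 1 and 6 correlate 0.7 and the other pairs 0.5. Under the three-level reading only, the 1-week bias is (1 − 0.5) × 0.21 = 0.105 SD; at r = 0.7 the simulated value is 0.060 SD.
- *Extreme selection* (the lowest-scoring 10%, 20% or 30% of one arm all missing 6 weeks, true 6-week difference in gain 0.50 SD):

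| Loss depends on | Correlations (0–1 wk, 1–6 wk, 0–6 wk) | Completers only | Likelihood |
|---|---|---|---|
| baseline | 0.5, 0.7, 0.4 | 0.62, 0.71, 0.80 | 0.50 |
| 1-week score | 0.5, 0.7, 0.4 | 0.46, 0.43, 0.41 | 0.50 |
| baseline | all 0.6 | 0.58, 0.64, 0.70 | 0.50 |
| 1-week score | all 0.6 | 0.50, 0.50, 0.50 | 0.50 |

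The direction and size of the bias depend wholly on the assumed mechanism, and one mechanism gives none.

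**The case against.** The strongest reply is that the gap is silence rather than a wrong method. The SPSS procedure is not named, and a group-by-time layout can be fitted to long-format data with a random subject effect, which keeps partial records. This stands to the extent that completer analysis is the likely default and not a documented rule. But a likelihood model is not what a split plot ANOVA ordinarily means, and the plan mentions none. If one was intended, the same edit settles it.

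The gain is also small where the reading is least disputed: about 1.5–2.5% in SE for two-visit outcomes and about 3% for the 6-week SRS-22. That stands. So does the point that attrition is unknown and one-armed selective loss is assumed. The Study Protocol section says patients were blinded to the randomisation result, which weakens, without excluding, the argument that reasons for leaving differ by arm.

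The SAP's independent-sample t test would use available cases. However, the plan assigns it to no follow-up outcome, and sends all five named scales to the split plot ANOVA.

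A reader might infer that a child who misses 6 weeks vanishes from the trial's analysis with everything already collected. The documents do not support this: the four outcomes measured to 1 week are fitted separately and keep that child. A reader might also infer that valid 1-week SRS-22 scores are certainly discarded. That needs a three-level model, which the wording permits but does not state.

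**Conclusion.** The point holds in a limited form. On the usual reading of the stated method, each outcome's comparison is likely to be restricted to children with every visit in that outcome's model, and nothing in the plan offsets this. The documents do not show that the results are biased, or that any child was lost. With full follow-up the effect is zero.

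At an assumed 20% random loss, the avoidable cost is about 2–3% in SE for two-visit outcomes and the 6-week SRS-22. A 1-week SRS-22 contrast has an SE about 12% larger than necessary, under the three-level reading alone. The bias that a better model would remove requires loss related to observed scores differently in the two arms. In the illustrations the 6-week bias runs from 0 to 0.04 SD under moderate selection, and up to 0.30 SD (0.80 − 0.50) under extreme selection. Confidence in the mechanism is good. No single magnitude can be claimed for this trial. It is a cheap improvement, not a fatal defect.

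**What to change.** Make the main analysis of each outcome a likelihood-based linear mixed model for repeated measures (SPSS MIXED), with these features:
- Fixed effects for group, visit and group-by-visit; unstructured within-patient covariance; a small-sample degrees-of-freedom method.
- Every randomised child with any observed assessment, in the arm assigned.
- For SRS-22, all visits at which it was collected. State which these are and how many time levels its model has.
- The completer split plot ANOVA kept as a sensitivity analysis, and missing visits reported by arm and visit.

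The cost is one paragraph of SAP text and a different procedure in the same package, with no extra patients, visits or measurements. The downside is reliance on data being missing at random given the observed scores. That is weaker than what the completer analysis needs, but the model does not protect against loss that depends on the unseen score itself.
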